11.6. Recording Adverse Events

All AEs regardless of causality will be recorded in the EDC from the time the participant signs the ICF through the participant's last visit or 28 days post last dose, whichever is longer. AEs that occur after signing of the ICF but prior to IP administration should be recorded on the Medical and Surgical History eCRF. AEs reported during this time that are serious should also be reported as an SAE (Section 11.7.1). Any clinically significant findings as determined by the Investigator, or changes from the time of signing the ICF, should be recorded on the AE or Medical History eCRF, as applicable.

For participants who received IP, if an Investigator becomes aware of an SAE that occurs after the participant's trial participation ends and the Investigator considers the event to be possibly

related to the IP, the Investigator should report the SAE to the Sponsor as described in Section 11.7.1.

11.7. Safety Reporting to the Sponsor of Serious Adverse Events and Other Safety Reports

11.7.1. Serious Adverse Events

If the Investigator determines that an event meets the protocol definition of an SAE due to any cause that occurs during the course of this trial, regardless of relationship to IP, he/she must notify the Sponsor by entering the SAE information into the eCRF within 24 hours of the Investigator becoming aware of the SAE.

If EDC is not available, the Investigator must complete a Safety Reporting Form and email it to the Sponsor **within 24 hours** of the Investigator becoming aware of the SAE. The Investigator must also enter the SAE information into the eCRF as soon as possible thereafter.

Sponsor Safety Reporting Email Address: [contact]

In the initial email, the Investigator must provide to the Sponsor the following eCRF pages, completed to the greatest extent possible:

- AE record.
- Medical history.
- Prior and concomitant medications.

Also, the following documents are to be forwarded: any laboratory results, diagnostic test results, or medical reports relevant to the SAE.

The EDC is the primary method for notification of SAE information. In rare circumstances and in the absence of email capacity, notification by fax or telephone is acceptable, with a copy of the Safety Reporting Form sent by overnight mail. Initial notification via telephone does not replace the need for the Investigator to complete the SAE information in the eCRF within the time frames outlined.

If the Investigator does not have all information regarding an SAE, he/she must not wait to receive additional information before notifying the Sponsor of the event. The SAE must be updated when additional information is received. Follow-up information received on all SAEs must be forwarded to the Sponsor using the same timelines as for an initial report.

11.7.2. Adverse Event of Special Interest

The Investigator must notify the Sponsor of any AESI that is serious (ie, an SAE) **within 24 hours** of the Investigator becoming aware of the event following the same reporting process as outlined for SAEs in Section 11.7.1.

For an AESI that does not meet the definition of an SAE, the Investigator must report it to the Sponsor **within 72 hours** of becoming aware of the event and following the same reporting process as outlined for SAEs in Section 11.7.1 by entering the information on the eCRF or utilizing the Safety Reporting Form, if the EDC is not available.

11.7.3. Drug-induced Liver Injury

The Investigator must notify the Sponsor **within 24 hours** of awareness that a participant has experienced DILI suspected to meet the Hy's Law following the same reporting process as outlined for SAEs in Section 11.7.1. The recommendations for the follow-up and handling of suspected DILI cases are provided in [Appendix K](#).

11.7.4. Unanticipated Adverse Device Effect

The Investigator must notify the Sponsor of any UADE. If a UADE is associated with an SAE, the Investigator must notify the Sponsor **within 24 hours** of the Investigator becoming aware of the effect following the same reporting process as outlined for SAEs in Section 11.7.1.

11.7.5. Reporting Pregnancy

Pregnancy is not considered to be an AE; however, if the outcome of a pregnancy meets the criteria for an SAE (ie, ectopic pregnancy, spontaneous abortion includes miscarriage and missed abortion, intrauterine fetal demise, neonatal death, or congenital anomaly [in a live-born baby, a terminated fetus, an intrauterine fetal demise, or a neonatal death]), the Investigator should follow the procedures for reporting SAEs. Female participants who become pregnant within 8 weeks after receiving IP should also notify the Investigator. The Investigator must attempt to follow the pregnancy to term or termination to report on outcome and health status of mother and child.

The Investigator must notify the Sponsor of any pregnancy by completing a Pregnancy Form and emailing it to the Sponsor **within 24 hours** after the Investigator becomes aware of the pregnancy.

Sponsor Safety Reporting Email Address: [contact]

11.8. Follow-Up of Adverse Events

After the occurrence of an AE, the Investigator is required to follow each participant proactively and provide further information on the participant's condition. All AEs documented at a previous visit or contact and designated as ongoing will be reviewed at subsequent visits or contacts.

Nonserious AEs will be followed after the last scheduled trial visit until the event resolves, the condition stabilizes, or until the event is otherwise explained or judged by the Investigator to be no longer clinically significant (unless the participant is lost to follow-up or withdraws consent).

SAEs will be followed until the event resolves (ie, when the event no longer meets any of the seriousness criteria), the condition stabilizes, or until the event is otherwise explained or judged by the Investigator to be no longer clinically significant (unless the participant is lost to follow-up or withdraws consent). The Investigator will ensure that follow-up information provided to the Sponsor includes results of any additional laboratory tests or investigations, histopathologic examinations, or consultations with other healthcare professionals that serve to clarify the nature of the event, the cause of the event, or both. New or updated information will be recorded as outlined in the section Reporting Serious Adverse Events to the Sponsor (see Section 11.7.1).

The Investigator will assess the outcome of each AE using the following categories:

- Resolved/Recovered: the AE resolved or the participant recovered without sequelae. An AE (either serious or nonserious) occurred and had an end date without a complication.
- Resolved/Recovered with sequelae: the AE has a complication or condition that results from a previous AE.
- Not resolved: at the end of the trial, a nonserious AE either has not changed in intensity or may not have recovered to baseline values.
- Unknown: the participant has withdrawn from the trial prematurely or is lost to follow-up, and the status of the event is unknown.
- Death.

12. PHARMACOKINETICS AND PHARMACODYNAMICS

12.1. Pharmacokinetics

Blood samples for PK assessments will be collected prior to administration of IP and post-dose at the specified timepoints (Table 5). Plasma samples for determination of rademikibart concentrations will be analyzed by a laboratory using a validated method.

Whole blood samples of approximately 2 mL will be collected and processed for measurement of plasma concentrations of rademikibart. Each plasma sample will be divided into 2 aliquots (1 for PK, and a backup).

Instructions for the collection and handling of biological samples will be provided by the Sponsor. The actual date and time (24-hour clock time) of each sample will be recorded.

12.2. Pharmacodynamics

Biomarkers of type 2 inflammation will be assessed over the course of participants' treatment including blood eosinophil count, eotaxin-3, C-reactive protein (CRP), total immunoglobulin E (IgE), and TARC as specified in the SoA (Table 5). Additionally, pulmonary and activation-regulated chemokine (PARC) and fibrinogen will be assessed.

Blood will be collected for measurement of these biomarkers of inflammation associated with COPD as specified in the SoA.

12.2.1. Fractional Exhaled Nitric Oxide

FeNO will be measured using a NIOX VERO[®] Airway Inflammation Monitor, or equivalent device according to the SoA (Table 5). The FeNO test will be performed prior to spirometry. Participants should not eat or drink for 1 hour prior to having the FeNO test.

If Visit 1b and Visit 2 are the same day, then FeNO does not need to be repeated.

Further details on the procedure for measuring FeNO with NIOX will be provided in a separate instruction manual

12.3. Immunogenicity

Immunogenicity will be evaluated by assessment of anti-drug antibodies (ADAs) and, if applicable, neutralizing antibodies (nAbs) according to the SoA (Table 5).

Antibodies to rademikibart will be evaluated in serum samples collected from all participants. Additionally, serum samples should also be collected at the final visit from participants who were withdrawn from the trial. These samples will be tested by the Sponsor's designee using validated methods.

Serum samples will be screened for ADAs binding to rademikibart and the titer of confirmed positive samples will be reported. Confirmed positive samples will be assessed for nAb and reported as nAb positive/negative.

13. STATISTICS

Complete details of the statistical analyses and methods, including data conventions, will be contained in a separate Statistical Analysis Plan (SAP) that will be finalized before database lock and unblinding. This section is a summary of the planned statistical analyses of the most important endpoints including primary and key secondary endpoints.

13.1. Primary Analysis Hypothesis

The null hypothesis is that there is no difference in the treatment failure rates between rademikibart treatment and placebo (rademikibart vs placebo).

H_0 : $P_{\text{rademikibart}} - P_{\text{p}} = 0$, where $P_{\text{rademikibart}}$ and P_{p} are the proportion of participants with treatment failure within 28 days after randomization for those randomized to rademikibart and placebo, respectively.

The alternative hypothesis is that rademikibart is different from placebo with respect to the treatment failure rate within 28 days after randomization.

H_a : $P_{\text{rademikibart}} - P_{\text{p}} \neq 0$.

13.2. Sample Size Determination

Approximately 160 participants with COPD exacerbation will be randomized using 1:1 allocation ratio to rademikibart 600 mg SC or placebo. The sample size calculation is based on the statistical analysis of the primary endpoint of treatment failure rate.

To account for a 5% dropout rate, approximately 160 participants will be randomized to ensure that 152 participants are evaluable. Assuming treatment failure rates of 22.5% for the rademikibart group and 45% for the placebo group up to 28 days after randomization, this sample size will provide at least 80% power to detect a difference at a 2-sided Type I error rate of 5%. Conditional power will be calculated during the IA and the final sample size will be determined according to the prespecified rules.

To ensure that the sample size is reasonably sufficient, an unblinded sample size re-estimation will be conducted when approximately the first 80 participants in total have had the opportunity to complete the trial or discontinue early (ie, no ongoing participants will be included in this sample size re-estimation procedure). The unblinded sample size re-estimation procedure for this trial will not allow for a reduction in the planned sample size or an increase in sample size greater than 40 participants per group (80 participants total). This sample size re-estimation procedure will be conducted by a statistician who is not associated with the conduct or final analysis of the trial. No penalty will be applied to the p-values or confidence intervals for assessing treatment difference from placebo due to this sample size re-estimation procedure. The independent statistician and DMC will recommend to the Sponsor any changes required to the sample size. Results from the IA will be communicated to a limited number of the Sponsor's senior management team who are independent of the clinical trial team and will be identified in the unblinding plan before the IA is performed.

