13.4.5. Primary Efficacy Endpoint

Formal hypothesis testing will be performed to analyze the difference in treatment failure rates between treatment groups within 28 days after randomization using the Cochran-Mantel-Haenszel test for the common risk difference stratified by severity of acute COPD exacerbation and baseline smoking status. The risk difference and the corresponding 95% CI will be presented. The null hypothesis of no difference in response rates between rademikibart and placebo will be tested against the 2-sided alternative that there is a difference at significance level 0.05. The primary efficacy analysis will be conducted based on observed data using the FAS.

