13.7. Interim Analysis

One IA is planned to be performed when approximately 80 participants with an acute COPD exacerbation have completed the Week 4 Visit. This analysis will allow for the potential adjustment of the sample size.

During the IA, the treatment failure rate will be assessed, the COPD exacerbation rate over the 4-week period will be assessed, and conditional power will be calculated by an independent statistician. The independent statistician will compare the calculated conditional power with the prespecified sample size and estimate the final sample size for the trial. The independent statistician and DMC will recommend to the Sponsor any changes required to the sample size. Results from the IA will be communicated to a limited number of the Sponsor's senior management team independent of the clinical trial team; these people will be identified in the unblinding plan before the IA are performed.

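### The protocol rules out any adjustment after an unblinded, conditional-power-driven sample size increase without limiting when N may rise, so the two-sided 5% level of the primary test is not guaranteed

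*Protocol*

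**What the plan says.** - **Design (Section 13.2).** "Assuming treatment failure rates of 22.5% for the rademikibart group and 45% for the placebo group up to 28 days after randomization", the protocol claims that "this sample size will provide at least 80% power to detect a difference at a 2-sided Type I error rate of 5" per cent. "To account for a 5% dropout rate, approximately 160 participants will be randomized to ensure that 152 participants are evaluable".
- **Re-estimation (Section 13.2).** It is unblinded, takes place at about 80 participants and uses conditional power. N may not fall and may rise by at most 40 per group, so the final total lies between 160 and 240. The final N is said to follow rules set in advance; the rules are not given. The paragraph then says "No penalty will be applied to the p-values or confidence intervals for assessing treatment difference from placebo due to this sample size re-estimation procedure".
- **Primary test (Section 13.4.5).** A stratified CMH test in which the null hypothesis "will be tested against the 2-sided alternative that there is a difference at significance level 0.05", reported with a 95% confidence interval.
- **Decision step (Section 13.7).** "The independent statistician will compare the calculated conditional power with the prespecified sample size and estimate the final sample size for the trial". The Synopsis, under Statistical Methods, says nearly the same.
- **Multiplicity (Section 13.4.2).** Covers only secondary and exploratory endpoints.

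No section names a lower limit for conditional power, a target, a combination statistic or an argument that the Type I error is preserved.

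**The concern.** When N is increased because of the observed treatment effect, the ordinary final statistic reweights the two stages. A larger second stage shrinks the weight of the first. If the interim result is weak, this dilutes bad luck and raises the chance of a false positive. If the interim result is already promising, the same increase lowers it. The unadjusted test therefore keeps its level under some increase rules and not under others.

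The no-penalty sentence is the conclusion of an argument whose condition, a restriction on when N may rise, the protocol does not state. At stake are the level of the single primary test and the coverage of its 95% interval, both of which the protocol presents as exactly 5% and 95%.

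**Working it through.** **1. The plan's own figure.** With 76 per arm, rates 0.225 and 0.45 and mean rate 0.3375:

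- SE under the null = sqrt(2 × 0.3375 × 0.6625 / 76) = 0.0767
- SE under the alternative = sqrt((0.225 × 0.775 + 0.45 × 0.55) / 76) = 0.0745
- Power = Φ((0.225 − 1.96 × 0.0767) / 0.0745) = Φ(1.00) = 84.2%

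The claim of at least 80% holds. 152 / 0.95 = 160, so the dropout allowance is also right.

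**2. Set-up for the Type I error.** Interim at n1 = 80, final N between 160 and 240 (Section 13.2), conventional Z against 1.96 (Section 13.4.5). Let z1 be the interim Z (positive = benefit) and t = 80/N. Under the null, the chance of crossing 1.96 at the end given z1 is 1 − Φ((1.96 − z1·√t) / √(1 − t)).

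- N = 160 (t = 1/2): 1 − Φ(2.772 − z1)
- N = 240 (t = 1/3): 1 − Φ(2.400 − 0.707·z1)

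The two are equal at z1 = (2.772 − 2.400) / (1 − 0.707), which is 1.268 before rounding. Below that value, raising N to 240 increases the false-positive chance (at z1 = 0.5, from 1.2% to 2.0%). Above it, raising N lowers it (at z1 = 1.5, from 10.2% to 9.0%).

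Conditional power at N = 160 under the observed trend is Φ(2·z1 − 2.772), which at z1 = 1.268 is Φ(−0.235) = 0.407.

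**3. Overall two-sided level.** The conditional probability, both tails, is integrated over the null distribution of z1. The increase rules are assumptions, because the protocol gives none.

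| Rule (conventional test at 1.96) | Level |
|---|---|
| Fixed N = 160 | 5.00% |
| Trend conditional power < 0.80: raise to 240 | 5.31% |
| Trend conditional power < 0.80: smallest N reaching 0.80, else 240 | 5.34% |
| Trend zone 0.05–0.80 (to 240 / smallest N) | 5.07% / 5.11% |
| Trend zone 0.10–0.80 | 5.01% / 5.04% |
| Trend zone 0.20–0.80 | 4.95% / 4.98% |
| Trend zone 0.41–0.80 | 4.92% / 4.95% |
| Design-effect conditional power 0.10–0.80: raise to 240 | 5.64% |
| Worst choice of N at every z1 | 5.79% (one-sided 2.90%) |

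The design-effect row shows that a floor means little unless its scale is stated. With the planned drift of 0.225 / sqrt(2 × 0.3375 × 0.6625 / 80) = 3.009, the crossover z1 = 1.268 corresponds to design-effect conditional power Φ((0.707 × 1.268 + 0.5 × 3.009 − 1.96) / 0.707) = 0.73. A design-effect floor of 0.10 therefore admits many weak interim results.

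**4. Exact binomial check.** 40 per arm at interim, 80 or 120 per arm at the end.

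| Common failure rate | Fixed N | Raise when trend conditional power < 0.80 | Raise when \|z1\| < 1.268 |
|---|---|---|---|
| 22.5% | 5.12% | 5.38% | 5.90% |
| 33.75% | 5.11% | 5.30% | 5.83% |
| 45% | 4.70% | 5.03% | 5.48% |

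The excess over fixed N under the conditional-power rule is 0.19 to 0.33 percentage points, in line with the normal calculation. Stratification and dropout are ignored throughout.

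**The case against.** The strongest reply is that Section 13.2 does say N will follow rules set in advance, and that Section 13 calls itself a summary with full detail in the SAP. A conditional-power zone is commonly kept in the SAP or the DMC charter. If the rule there has a suitable floor, the level is about 5% or less and the no-penalty sentence is correct as it stands. This is right as far as it goes: the absence of a numeric zone is not the finding, and a reader should not infer that no rule exists. What remains is that the protocol commits to no adjustment whatever the rule is. A SAP with a weighted test would depart from Section 13.2. The protocol requires the SAP before database lock and before the code is broken for the primary analysis, not before the interim look.

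Three stronger readings are tempting and not supported:

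- **That the true level is 5.8%.** That bound requires raising N to 240 whenever |z1| < 1.268, including when the drug looks harmful, and not raising it at trend conditional power 0.41–0.80, where such a rule would normally act. None of the conditional-power rules examined reaches it.
- **That a floor of 0.41 is necessary.** It makes each single increase conservative, which is sufficient. Trend floors of 0.10 to 0.20 already give 4.95–5.04% overall.
- **That the sponsor sees arm-level data while choosing N.** Section 13.2 says "Results from the IA will be communicated to a limited number of" senior managers outside the trial team, and Section 8.4.3 lists them as exceptions to blinding, so unblinded results are plausible. But neither the content nor the timing is stated, and the recommendation on N comes from the independent statistician and the DMC.

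**Conclusion.** The point holds as a should-fix. As written, the protocol pairs an unconditional no-adjustment statement with an effect-driven increase of up to 50% (80/160) and an ordinary test at 0.05, and contains nothing that makes this combination valid. The two-sided 5% level is not guaranteed.

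The size is modest: about 0.3 percentage points for a trend-based rule aiming at 80% with no floor, at most about 0.8 points for any choice of N within the stated limits, and none if increases require trend conditional power of about 0.2 or more. These figures assume an interim at exactly half the planned information and a cap of 240. Which one applies depends on a rule that the protocol does not show.

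Separately, Section 13.7 and the Synopsis compare a probability with a sample size. That sentence cannot serve as a decision rule, whatever the SAP contains.

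**What to change.** Make one of two changes before the interim analysis.

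(a) Define the primary test as a combination of stage-wise CMH statistics with pre-fixed weights sqrt(0.5) and sqrt(0.5) (Cui-Hung-Wang), with a matching confidence interval. This holds 5% under any increase rule. At the planned effect, with increases towards 80% conditional power and no floor, power is 92.8% against 93.7% for the conventional test, a cost of under 1 point.

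(b) Keep the conventional test, but make the no-penalty sentence conditional on a stated, binding conditional-power zone. State the effect assumption used (observed trend or design effect) and a lower limit shown to keep the overall level. A trend-based limit of about 0.41 at N = 160 makes every increase individually conservative; a smaller limit is acceptable if the overall level is demonstrated. The price is power: with the 0.41 floor, conventional power at the planned effect is about 87.3%, against 93.7% with unrestricted increases and 85.3% with N fixed at 160.

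Under either option, reword Section 13.7 and the matching Synopsis sentence so that conditional power on the primary endpoint is compared with a target conditional power. The work is wording in the protocol, SAP and DMC charter; no trial procedure changes.

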13.3. Analysis Sets

For the purposes of analysis, the following analysis sets are defined:

Analysis Set	Description
RS	All participants who are randomized to treatment.
FAS	All participants from RS having taken at least 1 dose of IP after randomization; data will be presented based on randomized treatment group.
PPS	All participants from FAS without important protocol deviation(s) that could affect the evaluation of the IP.
SS	All participants from RS having taken at least 1 dose of IP after randomization; data will be presented based on treatment actually received.
PKS	All participants from RS with at least 1 dose of rademikibart taken and with at least 1 post-dose evaluable PK blood sample.

FAS = Full Analysis Set; IP = investigational product; PKS = Pharmacokinetics Analysis Set; PPS = Per-Protocol Set; RS = Randomized Set; SS = Safety Analysis Set

All screened participants will be accounted for in the clinical study report (CSR). The inclusion and/or exclusion of participants from the trial analysis sets will be documented in the SAP before breaking the randomization code.

Participants in the Randomized Set (RS) will be summarized according to the treatment group to which they were randomized.

Participants in the Full Analysis Set (FAS) will be summarized according to the treatment group to which they were randomized, regardless of treatment received. The primary analyses of all efficacy endpoints will be conducted in the FAS.

Supportive efficacy analyses will be conducted in the Per-Protocol Set (PPS). Analyses based on the PPS will be performed to support the results obtained for the FAS. Reasons for exclusion from the PPS will be documented prior to database lock and unblinding.

The analysis population for the safety endpoints will be the Safety Analysis Set (SS). These participants will be analyzed according to their actual treatment received, regardless of the randomized treatment assigned.

The analysis population for the immunogenicity endpoints will be the subset of Pharmacokinetic Analysis Set (PKS) population with at least a predose (baseline) and at least one evaluable post-dose immunogenicity assessment.

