9. INVESTIGATIONAL PRODUCT MATERIALS AND MANAGEMENT

9.1. Investigational Product

The rademikibart drug product is formulated as a liquid sterile solution at 150 mg/mL in 10 mM L histidine, 60 mM trehalose, and 100 mM NaCl with 0.02% polysorbate 80 at pH 6.2. It is provided as a colorless-to-pale yellow sterile solution at 150 mg/mL concentration in a 1 mL single-dose PFS that delivers 1.0 mL solution.

Placebo solution is identical in appearance and content to the active solution except for rademikibart.

All IPs (rademikibart and placebo) will be supplied as a sterile PFS with a pre-assembled needle safety device. Each PFS is intended for a single 1 mL dose (150 mg) administered subcutaneously.

The individual IP information is presented in [Table 4](#).

Table 4: Investigational Products

Intervention Name	Rademikibart	Placebo
Intervention Description	Novel anti IL-4R α human monoclonal antibody	Matched-volume placebo
Formulation	Injection	Injection
Unit Dose Strength(s)	150 mg in 1 mL	Matching volume
Dosage	600 mg (4mL) 4 injections	Matching volume 4 injections
Duration of Treatment	Single-dose administration	Single-dose administration
Route of Administration	Subcutaneous injection	Subcutaneous injection

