13.4.9. Anti-drug Antibodies

ADA status (positive vs negative) at each visit will be summarized by treatment group. If considered relevant, descriptive statistics including number of participants, mean, standard deviation, median, and range of the actual ADA titers by treatment group and visit will be provided. The ADA status across the trial for each participant (positive vs negative) will also be classified and summarized by treatment group.

The association of ADA status across the trial (positive vs negative) with AEs/SAEs may be evaluated. In addition, the association of ADA titers (\geq median titer in positive participants vs $<$ median titer) with AE/SAEs may be evaluated for ADA-positive treated participants only. The ADA-positive participants across the trial may also be divided into persistent positive vs transient positive. A participant will be considered as persistent positive if he/she has positive ADA for ≥ 2 consecutive visits with ADA assessment. Otherwise, the participant will be considered as transient ADA-positive. The associations between ADA and AE/SAEs may be summarized for both persistent positive participants vs transient positives participants.

Evaluations of nAb will be conducted on those serum samples that test positive for ADA. The test sample is deemed positive or negative for the presence of nAb to rademikibart relative to a predetermined (in assay validation), statistically derived cut point.

All participants with titer information will be listed.

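### Section 13.3 builds the immunogenicity set from the rademikibart-only PK set, so the ADA summaries by treatment group would have an empty placebo column

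*Protocol*

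**What the plan says.** The analysis-set table in Protocol Section 13.3 defines the PKS as "All participants from RS with at least 1 dose of rademikibart taken and with at least 1 post-dose evaluable PK blood sample". The text below the table then says "The analysis population for the immunogenicity endpoints will be the subset of Pharmacokinetic Analysis Set (PKS) population", with the further condition "with at least a predose (baseline) and at least one evaluable post-dose immunogenicity assessment".

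The same table words the Safety Set (SS) differently: "All participants from RS having taken at least 1 dose of IP after randomization; data will be presented based on treatment actually received". That definition turns on investigational product, which covers both arms. The PKS definition names rademikibart.

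Three other places presuppose placebo participants:

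- Section 12.3: "Antibodies to rademikibart will be evaluated in serum samples collected from all participants".
- Section 13.4.9: "ADA status (positive vs negative) at each visit will be summarized by treatment group", and also "The ADA status across the trial for each participant (positive vs negative) will also be classified and summarized by treatment group".
- The immunogenicity entry under Statistical Methods in the synopsis, which plans incidence and duration of treatment-emergent ADAs and nAbs by treatment group.

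Table 2 in Section 5 lists immunogenicity among the exploratory objectives.

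**The concern.** A set restricted to people who took rademikibart cannot supply a placebo column, yet the protocol plans its ADA tables by treatment group. A programmer following Section 13.3 would produce tables with one empty arm. A programmer following Section 13.4.9 would have to depart from the stated set.

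What is at stake is how ADA incidence on rademikibart is read. Some participants may become ADA-positive after baseline without any drug cause, for example through assay false positives. The placebo arm is the internal estimate of how often that happens. Without it in the summaries, the treatment-emergent incidence on rademikibart stands alone.

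A smaller consequence follows from the same definition. A rademikibart participant with usable predose and post-dose ADA results but no evaluable post-dose PK sample is also left out.

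**Working it through.** **Inputs**

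- About 160 participants randomized, 152 evaluable, 5% dropout (Section 13.2).
- 1:1 allocation (Sections 8.4.2 and 13.2).
- Sample size re-estimation can add at most 40 per group (Section 13.2).
- PKS, SS and immunogenicity set definitions (Section 13.3).
- Placebo composition (Section 9.1): "Placebo solution is identical in appearance and content to the active solution except for rademikibart".

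**The plan's headcount**

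152 / (1 − 0.05) = 160, which agrees with the stated number randomized. At 1:1 this is 160 / 2 = 80 per arm randomized and 152 / 2 = 76 per arm evaluable.

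**Set logic**

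1. The immunogenicity set is contained in the PKS (Section 13.3).
2. The PKS is contained in the participants with at least one dose of rademikibart (Section 13.3).
3. Placebo contains no rademikibart (Section 9.1), so someone who received only placebo is outside the set in step 2.
4. Hence the immunogenicity set contains no one who received only placebo.

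A participant randomized to placebo who was given rademikibart in error could enter the PKS. The statement is therefore about those who received only placebo, not everyone randomized to placebo.

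**Size**

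| | Placebo participants available | In the immunogenicity set as written |
|---|---|---|
| Randomized, planned size | 160 / 2 = 80 | 0 |
| After 5% dropout | 152 / 2 = 76 | 0 |
| Randomized, maximum increase | 80 + 40 = 120 | 0 |

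The first column is an upper limit on what a corrected set could include, because the predose and post-dose ADA conditions would still apply.

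**Passages side by side**

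| Place | What it implies for placebo |
|---|---|
| Section 12.3 | Sampled and evaluated |
| Section 13.4.9 and synopsis | Shown in the summaries |
| Section 13.3 | Excluded from the analysis set |

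No other part of the protocol defines a different immunogenicity set that would admit placebo participants.

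The number of rademikibart participants lost only for want of an evaluable PK sample cannot be computed from the protocol. It is probably small, because footnote q to Table 5 allows PK and ADA/nAb samples to be taken together when their collection days coincide.

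**The case against.** The strongest reply is that an exposed-only set may be intended and that the by-group wording was simply carried over. The Table 2 immunogenicity objective is to evaluate incidence and, unlike the efficacy objectives, does not mention a comparison with placebo. Section 13.4.9 promises summaries, not a test between arms. That is a possible intention, but it does not remove the contradiction, since an exposed-only set would leave the by-group wording without a purpose. Section 13.4.9 also limits one optional titer analysis to treated ADA-positive participants, a limit that would add little if the whole set were already rademikibart-only.

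It can also be said that the SAP will settle this. Section 13.4.1 does allow changes to be described in an amendment, the SAP or the study report. But the protocol states the set itself, so an SAP that admits placebo participants would be departing from it, not filling a gap.

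Several stronger inferences are tempting and are not supported:

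- **That pre-existing reactivity could not be separated from drug-induced antibodies.** The set requires a predose assessment, Table 5 footnote q places the Day 0 sample before dosing, and the endpoint is treatment-emergent. Each participant's own baseline handles this. What remains is new post-baseline positives without a drug cause.
- **That a count of such positives can be given.** The documents state no background rate. Applying an assumed confirmed-positive rate to the 80 rademikibart participants would also ignore the baseline sample and the treatment-emergent definition.
- **That placebo ADA data are lost.** Samples are collected regardless, and Section 13.4.9 also plans a listing of all participants with titer information, which is not expressly limited to the PKS. The loss is in the summaries.
- **That a PK sample has no bearing on an ADA result.** Drug concentration can help interpretation. The supportable statement is only that Sections 12.3 and 13.4.9 do not make a PK sample a condition for classifying ADA status.

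**Conclusion.** The concern holds as an internal contradiction. By the definitions in Section 13.3, none of the roughly 80 participants expected to receive only placebo (up to about 120 after the largest permitted increase) can enter the immunogenicity set, while the synopsis and Section 13.4.9 require summaries by treatment group. The practical effect is a placebo column with N = 0 and no summarized placebo rate of new post-baseline positives against which to read incidence on rademikibart.

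The reach is narrow. The endpoint is exploratory and summarized descriptively. Efficacy analyses, the safety tables on the SS, alpha and power do not depend on this set. The conclusion rests only on the protocol's wording, the 1:1 allocation and the planned number randomized. It is worth correcting because the rule is wrong as written and the repair costs almost nothing.

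**What to change.** In Section 13.3, replace the sentence on the immunogenicity population. Define the set as all SS participants in both arms, analyzed by treatment actually received, who have a predose and at least one evaluable post-dose ADA assessment. Remove the link to the PKS. This also retains any rademikibart participant with ADA data but no evaluable post-dose PK sample.

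If an exposed-only set is truly intended, the alternative is to keep Section 13.3 and remove the by-treatment-group wording from the synopsis and Section 13.4.9. That gives up the placebo reference although the samples will have been taken.

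The cost of the preferred change is one sentence, carried through to the SAP. It needs no new samples, visits or participants. It should be made before unblinding, so that the choice of population cannot be influenced by the ADA results.
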